European Society of Cardiology conclusively demonstrated that surgical occlusion of the LAA markedly decreased the risk of stroke in comparison to controls: at 3.7 years 6% in patients with no LAA versus 18% in the control population(42).

[figure not shown]

Figure 2. Pulmonary vein isolation procedure

Hypothesis

We hypothesize that performing a prophylactic limited left sided surgical maze, i.e., pulmonary vein isolation and excision of the left atrial appendage, in a group of at risk cardiac surgical patients at the time of the index procedure, will reduce the incidence of POAF. The null hypothesis is that the prophylactic surgical ablation will have no effect on the incidence of POAF.

Setting of the Research

This study will be conducted at a single center, Spectrum Health. The PI and all Spectrum Health cardiothoracic surgeons participating in the study are highly qualified and certified by the American Board of Thoracic Surgery. They are all proficient in performing the maze procedure as it is commonly utilized in everyday practice to manage and treat AF.

Subjects will be seen in the cardiothoracic surgeon's office and/or the hospital inpatient setting. The surgery will be performed at the Meijer Heart Center, Spectrum Health Hospitals.

Resources Available to Conduct this Research

Spectrum Health cardiothoracic surgeons perform approximately 1200 heart surgeries per year. Approximately 300 of these surgeries which include isolated coronary artery bypass grafting (CABG), isolated aortic valve replacement (AVR), or combined AVR/CABG are performed in patients ≥ 70 years of age. Therefore, we do not anticipate difficulty recruiting the necessary number of subjects during the enrollment period.

The PI will have dedicated research time in his schedule. Experienced research staff from the CV Structural Heart Team will assist with the study as delegated by the PI.

Study Design

This is a single-center, prospective, randomized, unblinded, interventional feasibility study to determine whether or not a prophylactic limited left sided surgical maze procedure is effective in reducing or preventing POAF. A high risk population with no history of atrial fibrillation or flutter, with a baseline risk of POAF of 40% or greater will be chosen. This includes CABG/AVR, isolated AVR, and isolated CABG patients 70 years and older. Up to 60 subjects who are scheduled to undergo elective open heart surgery will be randomized 1:1 into one of two study arms:

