- 7. Subjects currently on antiarrhythmic drugs Class I and III including amiodarone.

Study endpoints

The incidence or absence of documented AF, defined by Society of Thoracic Surgeons (STS) registry data as the occurrence of POAF or atrial flutter that requires treatment, is the primary endpoint (21). In addition, length of stay (LOS) and additional antiarrhythmic or anticoagulant medications will be examined as a secondary endpoint.

Safety endpoints

The safety endpoint is the occurrence of one of the following events between time of procedure and the 30 day post procedure assessment:

- All-cause death
- TIA/stroke
- Bleeding (chest tube drainage) that is procedure related and requires take back to the operating room or blood transfusions
- Incidence of AF
- Need for permanent pacemaker
- Evidence of pulmonary vein stenosis defined as > 50 % occlusion of the vessel.

Procedures Involved in the Research

Baseline preoperative cardiac surgery workup will be done on all patients according to standard of care. This workup will consist of:

- History and physical exam
- Chest X-Ray

- Electrocardiogram
- Echocardiogram
- Cardiac catheterization
- Blood and urine tests such as complete blood count, complete metabolic count, cardiac enzymes, type and screen, and urinalysis. Any other indicated tests based on patient history and index procedure i.e.; pulmonary function tests, carotid ultrasound, leg vein mapping, noncontrast chest CT.

Prior to enrollment, the protocol and informed consent must be approved by the Spectrum Health Institutional Review Board (IRB). IRB approved Health Insurance Portability and Accountability Act (HIPPA) will also be used. A regulatory binder and subject binders will be created according to local requirements and stored in the CV Research Department.

Before the subject signs the informed consent form (ICF), the investigator or designated study personnel will explain the research, study procedure, anticipated benefits, and potential risks of study participation. Adequate time will be allowed to read the ICF and ask questions. The original signed ICF will be kept with the subject's research records and a copy will be given to the subject.

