Adverse events reporting will include the categories of cardiac, respiratory, vascular, bleeding, neurological (stroke/TIA), other organ complications and infection. Adverse events will be monitored by research staff and the investigator from the time of cardiac surgery until 365 days post procedure. AEs will be categorized according to seriousness and device and/or procedure relatedness. The monitoring of adverse events will occur from the time of cardiac surgery, throughout the hospitalization, at the 30 day, 6 week +/- 7 days, 6 months +/- 7 days and 12 months +/- 7 days post procedure assessments.

Serious adverse events or serious adverse device-related events will be reported to the FDA and Spectrum Health IRB per the regulations and reporting procedures.

If any thromboembolic events are observed during the study, an adverse event form will be submitted to the FDA. This report will include anonymized information on the procedure, type, and severity of thromboembolic event, the patient specific anticoagulation protocol, and the total number of subjects enrolled and treated in each arm by the event time.

Adverse events will be reported and recorded in REDCap and will include the following information:

- Date of onset first observation
- Description of event
- Seriousness of event
- Causal relationship to device/procedure
- Treatment required
- Outcome/resolution

The investigator and the non-study cardiothoracic surgeon will review all AEs.

For the purposes of this study certain events will be considered part of the expected post-operative course and will not be reported unless the investigator feels they deviate from the norm:

- Post-operative pain requiring medication
- Temporary mental status changes (except TIA/stroke)
- Mild GI disturbances, i.e. decreased appetite, nausea, vomiting, constipation or diarrhea
- Respiratory findings post-surgery, including oxygen usage, pleural effusion, atelectasis
- Minor laboratory findings, including hypokalemia, hyperkalemia, hypocalcemia, hypomagnesemia, leukocytosis, thrombocytopenia, hyperglycemia
- Post-operative anemia d/t intraoperative blood loss/dilution requiring ≤ 2 U transfusion
- Low-grade fever < 38.5∘ C
- Hypo/hypertension requiring treatment
- Mild creatinine increase, ≤ 0.3 mg/dL

Provisions to Monitor the Data for the Safety of Subjects

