Data will be reviewed by a non-study cardiothoracic surgeon; [name]. The review will include subject eligibility, documentation of the consent process, adverse events, and subject withdrawals. Review will occur after every 5 patients have a completed surgical procedure and are discharged from the hospital. Adverse Events (AE) will be evaluated for seriousness, unanticipated, procedural and/or device-relatedness. If any Serious Adverse Events (SAE) occur beyond what is expected in this patient population and are thought to be related to the limited left sided surgical maze procedure, the FDA and Spectrum Health IRB will be notified per reporting practices and the study may be terminated.

Monitoring of patient data will continue throughout the study at the scheduled assessment times.

Withdrawal of subjects

We do not foresee any circumstances in which subjects would want to withdraw from the study. However, subjects may withdraw from this study at any point, it will not be held against them nor involve penalty or loss of benefits to which subjects are otherwise entitled.

Risks/Benefits to Subjects

Neither LAA amputation or pulmonary vein isolation ablation, the 2 components of the limited left sided surgical maze procedure, have been shown to pose additional risk to the subject over the primary open heart procedure (7,8,16,28).

Potential adverse events with this combined procedure are similar to the risks of cardiac surgery and are listed below as described in the AtriCure® Synergy Ablation System Instructions for Use:

- Death
- Excessive bleeding that may require re-intervention
- Cardiac tamponade
- Pulmonary vein stenosis
- Restrictive or constrictive pericarditis
- Infection that may result in sepsis or endocarditis
- Myocardial infarction (MI)
- Stroke or transient ischemic attack (TIA)
- Thromboembolism
- Diaphragmatic (phrenic nerve) paralysis
- Esophageal-left atrial fistula or esophageal rupture
- Atrial perforation or rupture
- Ventricular perforation or rupture
- Atelectasis
- Pneumonia
- Congestive heart failure
- Cardiac valve injury
- Persistent pneumothorax
- Excessive pain and discomfort
- Deep sternal wound infection (mediastinitis)
- Perioperative atrial or ventricular rhythm/conduction disturbance
- Pericardial effusion
- Injury to the great vessels
- Injury to unintended surrounding tissues, including tears and punctures
- Extension of cardiopulmonary bypass time or aortic cross clamp time

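### Bleeding counts toward the safety endpoint only if called procedure related, an undefined judgement in an unblinded trial with no masked adjudication described

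*Combined protocol and SAP*

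**What the plan says.** Safety endpoints lists six events. Five have no attribution test: death from any cause, TIA or stroke, AF, permanent pacemaker, and pulmonary vein stenosis above a stated threshold. The sixth is "Bleeding (chest tube drainage) that is procedure related and requires take back to the operating room or blood transfusions". The window for all six runs "between time of procedure and the 30 day post procedure assessment".

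Study Design states: "This is a single-center, prospective, randomized, unblinded, interventional feasibility study".

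On attribution, Adverse events says "AEs will be categorized according to seriousness and device and/or procedure relatedness" and "The investigator and the non-study cardiothoracic surgeon will review all AEs". Provisions to Monitor the Data for the Safety of Subjects adds, for the non-study surgeon's review, "Adverse Events (AE) will be evaluated for seriousness, unanticipated, procedural and/or device-relatedness". Neither section gives criteria for relatedness or describes review masked to arm. The same monitoring section ties FDA and IRB notification and possible termination to serious events that "are thought to be related to the limited left sided surgical maze procedure".

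Bleeding also appears in other places:
- Statistical Methods names re-operation for bleeding as a secondary outcome to be compared between groups, with no relatedness qualifier.
- Data management collects every bleeding complication.
- Procedures Involved in the Research has staff review chest tube drainage and transfusion beyond what is normal for these patients.
- Adverse events treats post-operative anemia needing up to 2 units as expected, and not reported unless the investigator thinks it departs from the norm.

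**The concern.** In a randomised comparison the control arm already supplies the background bleeding rate, so attribution adds nothing that the comparison needs. It does add a judgement that can differ by arm. Here the judgement has no criteria, and the plan does not say that those making it are kept unaware of the assignment. The protocol also records a prior expectation: Risks/Benefits to Subjects says that neither part of the maze has been shown to add risk, and puts its risk of any complication below 1%. That expectation could make it easier to attribute a treatment-arm bleed to something else. Equally, a surgeon alert to the new step could attribute bleeding to it more readily, so the direction of any bias is not known.

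Bleeding is a poor place for such a filter. The treatment arm alone has the left atrial appendage transected and sutured, and Risks/Benefits to Subjects lists bleeding among the risks that may come with the maze. Safety is part of the stated objective, and with 30 patients per arm a single event moves the observed rate by 1/30, or 3.3 percentage points.

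**Working it through.** **No figure to reproduce.** The plan gives no bleeding rate, no sample size calculation, and no test for the safety endpoint. The check is mainly of the text, and the arithmetic below is illustration only.

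**Step 1: what *procedure* means.** The word is not defined.
- *Index operation.* The endpoint window starts at the procedure in both arms. The 6-week, 6-month and 12-month follow-up is timed post procedure for every subject. The monitoring section counts completed surgical procedures across all patients. Each use must mean the operation that both arms have.
- *Maze.* Where the monitoring section means the maze, it names it in full: "thought to be related to the limited left sided surgical maze procedure". Controls receive neither component of it.

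The index-operation reading is favoured. A control bleed can then count, and nearly all qualifying chest tube bleeding would be procedure related. The filter removes little legitimately, but it leaves room for reclassification. If a coder carried over the maze sense, no control bleed could count.

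**Step 2: inputs.** From Sample Size Determination, 30 per arm; from Statistical Methods, a 0.10 level (sidedness not stated; two-sided assumed). Assumed: true rates of qualifying bleeding of 5% to 40%, equal in both arms, and the attribution shares shown. The test is Fisher's exact, chosen here because the plan names none for this endpoint.

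**Step 3: a small worked case.** A 10% rate gives 0.10 × 30 = 3 expected bleeds per arm.
- Index-operation reading, one treatment-arm bleed reclassified: 2/30 v 3/30, p = 1.00.
- Two reclassified: 1/30 v 3/30, p = 0.61.
- Maze reading, all treatment-arm bleeds called related: 3/30 v 0/30, p = 0.24.

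None signals at 0.10. What changes is the observed difference: truly equal counts become unequal.

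**Step 4: range over rates.** With controls fixed at 0/30, 4 treatment-arm events give p = 0.112 and 5 give p = 0.052, so 5 is the threshold. For the maze reading the false-signal probability is P(X ≥ 5), with X binomial(30, rate × share called related). For the other columns, the two binomial probabilities are multiplied and summed over all tables with p < 0.10.

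| True rate, both arms | All qualifying bleeds counted | Index reading: all of one arm, half of the other | Maze reading: half called related | Maze reading: all called related |
|---|---|---|---|---|
| 5% | 0.7% | 0.8% | 0.1% | 1.6% |
| 10% | 2.6% | 4.9% | 1.6% | 17.5% |
| 20% | 4.6% | 16.2% | 17.5% | 74.5% |
| 30% | 5.6% | 28.4% | 47.6% | 97.0% |
| 40% | 5.2% | 41.7% | 74.5% | 99.8% |

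The index-reading column is the same whichever arm is under-counted. With milder unequal judgement (80% of one arm's bleeds counted, all of the other's), it is 2.7% at a 10% rate and 10.4% at 40%. Counting every qualifying bleed keeps the false-signal rate below the nominal 10% throughout.

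**Step 5: what can be recovered.** An all-cause count of re-operations is available from the secondary outcome and the collected bleeding data. Transfusion-only bleeds are less secure. The endpoint counts blood transfusions with no threshold, the daily review looks for need beyond normal, and the adverse event rule does not normally report anemia needing up to 2 units.

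**The case against.** The strongest case against is that this is one undefined word in one component of a 60-patient feasibility study, and that the plan's bleeding comparison has no filter at all. Much of that stands. Statistical Methods compares re-operations for bleeding between groups without attribution, although Study endpoints does not list that outcome. All bleeding complications are collected. The large false-signal rates in the table need high bleeding rates together with extreme attribution, in a test that the plan does not specify. If the six events are read as one composite, AF would dominate: at the 40% baseline risk in Study Design, 0.40 × 30 = 12 control patients would be expected to have it, and one or two reclassified bleeds would shift the total little.

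A reader might infer that control patients can never have the bleeding event. The documents do not support that as the plan's meaning: the endpoint's own lead-in and the follow-up schedule use *procedure* for the index operation, and the maze is spelled out where it is meant. A reader might also infer that those judging relatedness are known to be aware of the arm. The design is unblinded and no masking is described, but the documents do not say who classifies this endpoint or whether the non-study surgeon sees the assignment.

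None of this gives the qualifier a purpose. The unfiltered re-operation outcome does not repair the declared safety endpoint, and it does not cover transfusion-only bleeds.

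**Conclusion.** The concern holds in limited form. Bleeding is the only component of the safety endpoint that depends on causality. That judgement has no criteria, and no masked adjudication is described in an unblinded trial. On the favoured index-operation reading, the qualifier excludes little and leaves room for an assessor who may know the arm to reclassify a bleed, in either direction. Only if *procedure* were taken as the maze would the control count be zero by definition, and the text does not favour that.

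The effect is mainly on the declared safety endpoint and on transfusion-only bleeds. At an assumed 10% rate, one or two reclassified bleeds change the observed difference by 3.3 or 6.7 percentage points without approaching significance at 0.10. It would be wrong to conclude that the plan's bleeding comparison as a whole is biased, or that a false safety signal is likely. Those results appear only under assumed rates and attribution shares that the documents neither give nor imply. The change is still worth making, because it removes a possible source of bias at almost no cost.

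**What to change.** In Safety endpoints, delete the four words *is procedure related and* from the bleeding component. The limit to chest tube drainage and the re-operation or transfusion requirement stay as they are, and the sentence still reads correctly. State that the component is counted identically in both arms. Keep device and procedure relatedness as a descriptive adverse event field only.

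Reconcile the transfusion wording in Safety endpoints, in the daily review under Procedures Involved in the Research, and in the expected-event list under Adverse events, so that it is clear which transfused bleeds count and that they are recorded in both arms. Which threshold applies is for the investigators to settle.

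The cost is a short text amendment, with no new data for re-operations. Transfusions meeting the reconciled wording must be captured even when they are not reportable as adverse events. The downside is that a few bleeds unrelated to the maze will be counted. These may not be exactly equal between arms, for example if anticoagulant use differs because only the treatment arm has the pre-discharge echocardiogram.

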- 1. Control arm: Elective open heart surgery without a limited left sided maze procedure.
- 2. Treatment arm: Elective open heart surgery with a limited left-sided maze procedure.

Sample Size Determination

No sample size calculation was performed as this is a feasibility trial and the number is fixed at 60 patients where 30 will be randomly assigned to the control arm and 30 randomly assigned to the treatment arm.

Statistical Methods

Summary statistics will be calculated. Quantitative variables will be expressed as mean ± standard deviation or median [interquartile range]. Qualitative variables will be expressed as frequency (percent). To determine if there is an association in POAF and the two arms of the study, a Chi-Square Test or Fishers Exact test will be used depending on assumptions being met. To look at our secondary outcomes such as hospital length of stay and incidence of postoperative reoperations for bleeding, a two sample t-test or Wilcoxon Rank Sum will be used to determine if there is a difference between the two groups and those that had POAF vs. those that didn't. Significance will be assessed at the 0.10 level. A level of 0.10 will provide more power to the study while only allowing a slight increase in error.

Recruitment methods

All subjects who receive an inpatient or outpatient heart surgery consult and meet the criteria may be approached about study participation. Consults will occur in the Cardiothoracic Surgeon's office of the Meijer Heart Center or Spectrum Health inpatient units. The subject's electronic medical records (EMR), Cerner and Epic, will be reviewed. There are no plans for advertisement or patient payment related to study participation.

It is expected enrollment will take approximately 6 months.

Inclusion and Exclusion criteria

Inclusion Criteria

- 1. Male or female
- 2. Age \geq 70 years
- 3. Elective cardiac surgery: isolated AVR, isolated CABG, or AVR/CABG,

Exclusion Criteria

- 1. A history of AF or atrial flutter
- 2. Less common cardiac operations such as aortic root replacements, aortic dissections, myxoma excisions, or pericardectomies. Beating heart or off-pump procedures, redo open heart procedures.
- 3. Subjects with existing pacemaker and/or AICD
- 4. Vulnerable populations; adults unable to sign consent, prisoners
- 5. Need for emergent or salvage surgery for any reason
- 6. Currently participating in an investigational drug or another device study (excluding registries)

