All subjects will be on a beta-blocker preoperatively and throughout the hospitalization as per STS guidelines unless there is a clear contraindication. The use of amiodarone or other antiarrhythmic agents for prevention of POAF are not allowed. Should a patient experience POAF standard treatment with amiodarone or other agents may be utilized.

A 1:1 randomization will occur prior to surgery using REDCap to allocate subjects into the treatment (planned open heart surgery plus limited left-sided maze) or control arm (planned open heart surgery). The subject will be notified of their randomization assignment.

Care on the morning of surgery will follow current standards of care. Baseline vital signs will be obtained and the subject will be placed on telemetry. Vital signs such as blood pressure, heart rate and rhythm, central venous pressure, oxygen saturation will be monitored throughout the case as per standard of care.

After establishing cardiopulmonary bypass and myocardial arrest for the primary heart surgery procedure, the limited left sided surgical maze procedure will be performed on those patients who were randomized to the treatment arm of the study. An encircling lesion will be performed around the left atrial tissue just proximal to the entrance of both the left and right pulmonary veins utilizing the AtriCure® Synergy Ablation System according to Instructions for Use (IFU). The targeted tissue of the pulmonary vein will be placed between the distal and proximal jaws of the synergy ablation clamp ensuring that no tissue extends beyond the indicator line or into the jaw heel. The ASU2 is activated by pushing the footswitch. Once activated, the ASU2 emits a continuous audible tone indicating that current is flowing between the jaws of the clamp. When the tone turns to intermittent, it indicates tissue impedance has been met and the transmural lesion completed, then the footswitch is released. The system determines the minimum energy delivery needed to create a transmural lesion. This is based on tissue impedance and only that amount of energy will be delivered to the tissue (IFU). Time

needed to create a transmural lesion varies according to tissue thickness, composition, and the length of tissue within the clamp but averages 16 seconds (41).

No deviation from the IFU will occur, nor will the device be altered in any way.

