- Medications, pre- and post-op including name of medication, indication, dose.
- Procedure and date- including number of grafts and type of valve implanted
- CPB time, X-clamp time
- EKG rhythm(s), pre- and post-op (atrial flutter, SVT, VT, etc.)
- Post procedural stroke/TIA
- Post procedural MI
- Post procedural pacemaker implant
- Any bleeding complication
- Any incidents of POAF (date occurred, treatment used,)
- Length of stay

Data will also be collected at 6 weeks, 6 months and 12 months post-procedure. This will include:

- All adverse events
- Any rehospitalizations
- Medications, current and new
- Any episodes of AF or other cardiac arrhythmias
- EKG
- Need for pacemaker

• Echocardiogram: EF, valve gradients, left and right atrial function, pulmonary vein stenosis or presence of suspected thrombus.

In the event that we are unable to find subject information in the EMR at appointed study intervals, we may telephone subjects to inquire how they are and whether or not they have had any adverse events.

Assessments/procedures	Baseline	Hospitalization	Predischarge	Follow up	Follow up	Follow up
	Screening			6 weeks	6 months	12 months
				post	post	post
				procedure	procedure	procedure
				+/-7 days	+/- 7 days	+/- 7 days
Consent	Х					
History/Inclusion and	Х					
Exclusion						
Medication Review	Х	X		X	X	X
Randomization	Х					
AF occurrence and		X		X	X	X
treatment						
Transthoracic echo			X			
			Treatment			
			arm only			
Rehospitalizations				X	X	X
Adverse Events		X		X	X	Х

Adverse events

An adverse event (AE) is any untoward medical occurrence (signs, symptoms, abnormal laboratory findings) in a subject. It does not necessarily have to be caused by the device or procedure to be considered an adverse event.

A serious adverse event is one that led to death, serious deterioration in the health of the subject, resulted in a new hospitalization or prolonging the index hospitalization, a permanent impairment of a body structure or function, or required medical and/or surgical intervention to prevent further lifethreatening illness or injury

A device related adverse event is an event that in the investigators judgement may be related to the investigational device.

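### Randomization is set before surgery with no limit on the interval, although the arms differ only once bypass and arrest are established; allocating later and analysing everyone as randomized would cheaply remove avoidable bias

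*Combined protocol and SAP*

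**What the plan says.** - **Timing of allocation.** Procedures Involved in the Research states: "A 1:1 randomization will occur prior to surgery using REDCap to allocate subjects". In the assessment schedule at the end of Data management, the only mark in the row "Randomization" is under Baseline/Screening, the column that also holds consent and eligibility. No longest interval from allocation to surgery is given.
- **Disclosure.** The same section says: "The subject will be notified of their randomization assignment". It gives no day. The sentence stands before the description of care on the morning of surgery.
- **Where the arms diverge.** "After establishing cardiopulmonary bypass and myocardial arrest for the primary heart surgery procedure, the limited left sided surgical maze procedure will be performed", and only in the treatment arm. The workup and morning-of-surgery care are standard for everyone. The only other arm-specific item in the schedule is the pre-discharge echocardiogram.
- **Blinding.** Study Design declares it: "This is a single-center, prospective, randomized, unblinded, interventional feasibility study".
- **Background therapy.** "All subjects will be on a beta-blocker preoperatively and throughout the hospitalization as per STS guidelines unless there is a clear contraindication". Also: "The use of amiodarone or other antiarrhythmic agents for prevention of POAF are not allowed".
- **Eligible operations.** Elective isolated AVR, isolated CABG or AVR/CABG. The exclusions include "Beating heart or off-pump procedures, redo open heart procedures". No rule covers an operation that changes after allocation.
- **Withdrawal and analysis.** Withdrawal of subjects allows it at any time and expects none. Statistical Methods names a chi-square or Fisher's exact test at the 0.10 level, but no analysis population and no treatment of subjects who are randomized and then withdraw or have a different operation.

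**The concern.** Between allocation and bypass the plan lets the arm be known while some things are still open: whether the subject stays in the study, whether the operation is still an eligible one, and how the exception to beta-blockade is judged. A loss or change in this window comes after randomization, so it can differ by arm.

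Withdrawal is the most plausible route. Risks/Benefits to Subjects presents the maze as adding almost no risk and promising real benefit, and the consent discussion covers anticipated benefits. A subject who then learns that neither component will be performed has a reason to leave that a treatment-arm subject lacks.

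With 30 per arm, a few such subjects matter, and nothing in the analysis plan keeps them in the comparison. Nothing in either pathway, as described, needs the allocation at the baseline visit.

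**Working it through.** The plan has no power calculation or loss rate to reproduce. The only stated figure is 30 + 30 = 60 (Sample Size Determination).

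**1. Weight of one subject.** 1/30 = 3.3% of an arm. If 5-10% of subjects withdraw or change operation before bypass (an assumption), that is 0.05 × 60 = 3 to 0.10 × 60 = 6 subjects.

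**2. Loss of precision alone.** Take 0.10 two-sided (the plan does not state sidedness) and a control rate of 40% (Study Design). The CABG study cited under Risks/Benefits reports a 21% reduction without saying whether it is absolute or relative, so both are used. Losing 6 subjects evenly leaves 27 per arm. Power = Φ{[d√n − 1.645√(2p̄q̄)] / √(p₁q₁ + p₂q₂)}.

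| Comparison | n = 30 per arm | n = 27 per arm |
|---|---|---|
| 40% vs 19% (absolute) | 55.7% | 51.9% |
| 40% vs 31.6% (relative) | 16.6% | 15.7% |

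Balanced loss costs little. The issue is unbalanced loss.

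**3. Withdrawal, worst case.** Suppose the full data would be 12/30 control and 7/30 maze. The pooled rate is 19/60 = 0.317, z = 0.167/√(0.317 × 0.683 × 2/30) = 1.39, p = 0.165. Now drop three controls, none of whom would have had POAF: 12/27 = 44.4% against 7/30 = 23.3%, pooled 19/57 = 0.333, z = 0.211/√(0.333 × 0.667 × (1/27 + 1/30)) = 1.69, p = 0.091. The result crosses 0.10. The smallest expected count is 27 × 19/57 = 9, so the chi-square test applies.

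**4. How typical that is.** Before surgery nobody has a POAF outcome, so withdrawal cannot select on it directly. If the three controls leave at random, all three are POAF-free with probability (18 × 17 × 16)/(30 × 29 × 28) = 4,896/24,360 = 20%, and the expected control rate stays at 40%. If one of the three would have had POAF, the comparison is 11/27 vs 7/30: pooled 18/57 = 0.316, z = 0.174/√(0.316 × 0.684 × (1/27 + 1/30)) = 1.41, p = 0.158, and nothing crosses. Step 3 shows how fragile the result is; it does not estimate the bias.

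**5. Beta-blockade.** Background says that no preventive drug trial has shown better than a 20% reduction; take this as relative risk 0.80 (an assumption). With 40% POAF on the drug, the rate off it is 0.40/0.80 = 50%. If a fraction f of controls goes without it and the maze does nothing, the control rate is 0.40(1 − f) + 0.50f. Exact enumeration of the uncorrected chi-square test at 30 per arm gives:

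| f | Control rate | Chance of a false result favouring maze |
|---|---|---|
| 0 | 40% | 4.5% |
| 10% | 41% | 5.3% |
| 20% | 42% | 6.3% |
| 30% | 43% | 7.3% |

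The effect is small even under a large imbalance.

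**The case against.** The sponsor can fairly answer that the trial is openly unblinded, has 60 subjects and is a feasibility study, and that withdrawals before surgery are themselves feasibility data. It can add that telling subjects their arm lets them decline an irreversible appendage amputation, in people with no history of AF, knowing that it is coming. Both points stand. Disclosure is not a contradiction in the plan, and later allocation gives something up. But the plan also tests efficacy for significance, and small arms make each loss weigh more.

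Several stronger readings are tempting, and the documents do not support them:

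- *The arm is disclosed at baseline.* The day is not stated. The schedule has no day-of-surgery column, so its mark may mean only some time before the operation.
- *The ward team knows the arm.* Only the subject is said to be notified, and REDCap access is limited to approved study personnel.
- *Controls will be switched to off-pump surgery.* Off-pump procedures are excluded in both arms, and nothing indicates that conversions occur here. A converted patient would still be on telemetry until discharge, so the outcome could be observed.
- *Beta-blockade will drift by arm.* The drug is required in both arms, prophylactic antiarrhythmics are barred, and pre-operative medications with dose and indication are already collected.
- *Three withdrawals would reverse the conclusion.* That needs all three to be POAF-free. Withdrawal linked to prognosis is possible, but the documents give no evidence of it.
- *Allocation must wait until bypass is running.* That is not necessary, and it could add pump time, which the protocol lists as a risk.

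**Conclusion.** The point holds as a cheap improvement. Allocation comes earlier than the treatment requires, the interval is unlimited, the subject is told the arm (apparently before surgery), and no analyse-as-randomized rule covers what happens in between. Arm-dependent withdrawal is the main exposure; changes of operation come second, and the beta-blocker route is minor.

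The size cannot be estimated from the documents. One subject is 3.3% of an arm; an assumed 5-10% loss is 3 to 6 of 60; and three one-sided losses can move a borderline result across 0.10 only in an unfavourable configuration (about 20% under random loss). This rests on the natural reading that notification precedes surgery. If the sponsor already allocates and notifies on the day of surgery, the exposure is smaller and the missing analysis rule is what remains.

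A reader might infer that later allocation makes the comparison unbiased. It does not: the primary endpoint counts AF or flutter only when it is treated, and post-operative care stays unblinded.

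**What to change.** 1. Keep consent at baseline. Before allocation, record the planned operation and pre-operative beta-blocker status; the latter is already collected, so only its timing changes.
2. Open the REDCap allocation as late as practical: on the day of surgery, in the operating room before bypass, once the surgeon confirms that the case is still an eligible elective on-pump AVR, CABG or AVR/CABG. Amend Procedures Involved in the Research and the schedule to match.
3. State in the consent form that the subject will learn the assignment after surgery, and make consent to either arm explicit.
4. Add to Statistical Methods that all randomized subjects are analysed by assigned arm, with withdrawals and changed operations reported by arm and timing. This is worth adopting even if the timing of allocation stays as it is.

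**Cost.** Changes to protocol, schedule and consent wording, and REDCap access in the operating room. The clamp must be available for every enrolled case (the site reports using the system 200-250 times a year), and operating-room time must allow for either arm. The subject can no longer withdraw before surgery knowing the arm, which is why item 3 is needed.
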